Protocol for evaluating NOST follows the plan established for the implementation of NOST in Norwegian hospitals, as described in the National Standard for Hand Hygiene Observation. NOST will be implemented in the first quarter of 2023. All hospitals must, according to the Action Plan for Better Infection Control, use the solution and report data according to the standard. Participating in the evaluation of NOST is voluntary for the hospitals, and they do not need to decide on participation until later in 2023. However, we ask the hospitals to prepare for future evaluation. Therefore, we ask that the hospitals contribute the following upon the implementation of NOST:

- 1. The hospitals send an overview of which wards can implement NOST
- 2. The hospitals implement NOST in wards that are randomly selected to be intervention wards
- 3. The hospitals do not implement NOST in wards that are randomly selected to be potential control wards in the later evaluation of NOST

Points 1 and 2 are in line with the planned implementation of NOST and must be carried out by all hospitals regardless of participation in the evaluation study, while Point 3 is necessary preparation for the later evaluation of NOST. Hospitals will later in 2023 receive an invitation to participate in the evaluation of NOST. This will include an invitation to conduct a measurement of hand hygiene compliance in control wards, and approval for the NIPH to use data on infection occurrence and length of stay as outcome measures in addition to hand hygiene compliance.

Objectives

The objective of evaluating NOST is to:

- measure if implementation of NOST leads to increased compliance with hand hygiene recommendations, and
- measure if implemented NOST affects the epidemiology of HAIs in healthcare institutions and the length of hospital stays.

Methods

Study design and setting

This protocol includes the evaluation of NOST in hospitals. The evaluation is designed as a cluster-randomized controlled trial with two arms where eligible wards in hospitals are randomly allocated into an intervention and a control arm. NOST is implemented in the intervention wards at the start of the evaluation period, and compliance with hand hygiene and other outcomes are measured in both the interventions and control wards one year later.

Intervention

The intervention in the study is to implement NOST, which includes:

- observation and recording of compliance with hand hygiene recommendations

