- reporting the results back to the relevant wards
- identification of areas for improvement
- training or other actions taken to improve IPC in general or compliance with hand hygiene.

Thus, the intervention includes both observation of compliance and any additional improvement measures initiated as a result of the introduced NOST.

Observations of hand hygiene will be carried out in sessions of 20-30 minutes. During this period, all situations where hand hygiene is indicated (recommended) and whether hand hygiene is performed or not, are recorded. The number of hand hygiene indications during a session varies but will often be between 7 and 20.

When the intervention group has implemented and followed NOST for a year, we will measure compliance with hand hygiene recommendations, diagnosed HAIs and length of stay, in wards that have had NOST and in wards that have not introduced NOST.

The intervention arm will be followed over time with repeated measurements of both compliance with hand hygiene and other outcome measures, to see if the effect increases in line with implemented observations and quality improvement measures, or if the effect decreases during the study period.

Study populations

The evaluation of NOST in hospitals consists of two parts with different study populations. Part 1 is a quality improvement project and measures the effect in terms of increased compliance with hand hygiene recommendations. The study population in part 1 is employees with patient-related work.

In part 2, the occurrence of HAI and length of stay for hospitalized patients, and outbreaks of infectious disease among patients and staff are examined. When measuring HAI and length of stay, the study population is patients who are hospitalized in intervention or control units when the annual surveillance of HAI is conducted in the Norwegian Surveillance System for Antibiotic Use and Healthcare-Associated Infections (NOIS), together with all inpatients in the study period using data from the Norwegian Patient Registry (NPR). When measuring the number of outbreaks and the

number of secondary cases in outbreaks, the study population is both staff and inpatients in intervention or control wards during the outbreak periods.

Data collection and outcomes

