Hospitals will send the results of 30 hand hygiene observations from each included intervention ward every four months in accordance with the plan for the implementation of NOST in hospitals. The first submitted results will constitute the baseline measurement.

When NOST has been performed for a year, new measurements will be taken in the intervention wards and corresponding baseline measurements in the control wards. This will also include a minimum of 30 hand hygiene observations from each ward. The measurements in both arms will be conducted by observers who have received training and gained experience with NOST measurements during the year NOST has been carried out in the intervention wards.

The measurements from intervention wards that have had NOST for one year will be compared with contemporaneous baseline measurements in the control wards. The difference in compliance with hand hygiene in the intervention arm compared to the control arm will constitute the effect of having implemented NOST and performed quality improvement measures for one year. Repeated measurements over time in the intervention wards will be used to investigate whether the effect has increased and remains throughout the study period, or if the effect diminishes before comparison is made after one year.

The primary outcome is the number of measured indications for hand hygiene and the number of hand hygiene performed on indicated events, the proportion of correct compliance, and variation in correct compliance in the form of intra-class correlation coefficient (ICC).

Comparison of HAIs in the two arms will be made using surveillance data that is routinely collected from all hospitals. This includes:

- infectious disease outbreaks reported to the Norwegian Institute of Public Health's webbased outbreak notification system (VESUV), including the microbiological cause of the outbreak and the number of people infected among patients and staff
- number of patients recorded with infections in cross-sectional studies conducted in the Norwegian Surveillance System for Antibiotic Use and Healthcare-Associated Infections (NOIS)
- number of patients receiving antibiotic treatment recorded in NOIS
- number of patients recorded with postoperative infections in the surveillance of infections in surgical sites (NOIS-POSI)

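### Repeated compliance measurements in NOST wards alone cannot show whether the effect on hand hygiene compliance grows, lasts or fades, because control wards are measured once

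*Protocol*

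**What the plan says.** **Intervention wards** are measured repeatedly (Protocol, Data collection and outcomes): "Hospitals will send the results of 30 hand hygiene observations from each included intervention ward every four months". Of this series the protocol says: "The first submitted results will constitute the baseline measurement".

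**Control wards** are measured for compliance once, at one year (same section): "When NOST has been performed for a year, new measurements will be taken in the intervention wards and corresponding baseline measurements in the control wards". The Introduction agrees: "This will include an invitation to conduct a measurement of hand hygiene compliance in control wards".

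**The effect** is the difference between arms at that time: "The measurements from intervention wards that have had NOST for one year will be compared with contemporaneous baseline measurements in the control wards".

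**The use of the series** is stated twice. Data collection and outcomes: "Repeated measurements over time in the intervention wards will be used to investigate whether the effect has increased and remains throughout the study period", or whether it declines before the one-year comparison. The Intervention section says the intervention arm will be followed on compliance and on the other outcomes "to see if the effect increases in line with implemented observations and quality improvement measures, or if the effect decreases during the study period".

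**The SAP** assesses compliance at one year only (sections 4.1 and 5.1) and plans no interim or follow-up analyses (section 7.1). It has no time-course model (section 9) or estimand (section 10).

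**The concern.** By the protocol's own definition, an effect on compliance needs both arms measured at the same time. That happens once. At every earlier round only the NOST arm has a value, so there is no effect at those rounds whose later growth or decline could be seen.

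The documents themselves point to reasons other than NOST for the series to move. Rounds four months apart fall in different seasons. The rounds span a year in which practice may change for other reasons. The one-year observers are described as having gained their experience during that year, so earlier rounds were scored with less of it.

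At stake is a secondary but influential statement. Whether the benefit of NOST builds up or wears off could affect decisions to continue or intensify it. Followed as written, a background rise would be read as a growing effect and a background fall as a waning one.

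**Working it through.** **1. What is identified.** Let I(t) and C(t) be compliance in the two arms, and let the effect be E(t) = I(t) − C(t). Then

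I(t2) − I(t1) = [E(t2) − E(t1)] + [C(t2) − C(t1)].

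The protocol observes I at every round and C only at one year. C(t1) is missing, so the last bracket cannot be estimated. The error in the apparent change in effect equals the change the controls would have shown.

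**2. Illustration.** Take the planned one-year values, 0.60 and 0.40 (SAP section 6), so E = 0.20. Assume the NOST arm rose by 0.10 over the year, from 0.50.
- If background also rose by 0.10, controls began at 0.30. The first effect was 0.50 − 0.30 = 0.20: constant.
- If background was flat, controls began at 0.40. The first effect was 0.50 − 0.40 = 0.10: it doubled.
- If background rose by more than 0.10, the effect shrank.

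The observed data are the same in all three cases.

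**3. Size.** The hypothesised effect is 0.20 (Protocol, Sample size). No document gives a drift, so 0.03 to 0.10 over the year is assumed:
- 0.03 / 0.20 = 15%
- 0.10 / 0.20 = 50%

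**4. The plan's own figure.** Table 3 gives a detectable difference of 0.1961 at 26 wards per arm and 30 events per ward. The formula is (t0.975 + t0.80) × √(V × [1 + (m − 1) × ICC] / (m × g)).
- With m = 30 and ICC = 0.10, the design factor is 3.9/30 = 0.13.
- With V = 2 × 0.4 × 0.6 = 0.48 and df = 2(g − 1) − 2, the formula gives 0.140 at g = 26, which does not match.
- With V = 0.96 and df = 4(g − 1) − 2 = 98, it gives 0.1961. This variant fits all 25 cells within 0.0001, and 26 is its minimum (25 wards give 0.20002).

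Why the variance is doubled is not stated. It makes the sample size conservative and has no bearing on this point. The 26 wards serve below only as a setting.

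**5. How often drift would look like a changing effect.** This is a simulation of first-to-last change with a constant effect of 0.20 and the same drift in both arms. Assumptions: starting levels 0.55 (NOST) and 0.35 (control), ICC 0.10, 30 observations per ward and round, and 80% carry-over of ward effects between rounds. Entries are the share of trials with p < 0.05 for a change.

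| Drift over the year | NOST wards only, 26 | NOST wards only, 150 | Both arms, 26 per arm | Both arms, 150 per arm |
|---|---|---|---|---|
| 0 | 5% | 5% | 6% | 5% |
| 0.03 | 16% | 63% | 4% | 5% |
| 0.05 | 34% | 97% | 5% | 5% |
| 0.10 | 88% | 100% | 5% | 5% |

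In NOST wards alone the mean apparent change equals the drift. With concurrent controls it is about zero. As a check, the within-arm variance is 2 × (0.025 × 0.2 + 0.225/30) = 0.025 per ward, so the standard error at 26 wards is √(0.025/26) = 0.031. The normal approximation then gives 36% at a drift of 0.05, close to the simulated 34%. That 36% becomes 25% with 50% carry-over and 55% with full carry-over.

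The protocol expects several hundred wards (Group allocation). More wards make the false reading more likely, because bias does not shrink with sample size.

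**The case against.** The strongest reply concerns reach, and most of it stands.

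- **The SAP plans no such analysis.** The protocol defers detail to the SAP, which has no time-course model, estimand or table row. A reader might infer that a changing effect will be reported. The documents do not go that far: the SAP neither specifies nor withdraws the intention. The percentages in step 5 apply only if someone tests the within-arm change, and no document plans such a test.
- **It is not an objective.** The protocol's Objectives list compliance, the epidemiology of infections and length of stay. The time course appears only as a use of the data.
- **The main result is safe.** A reader might infer bias in the primary comparison. The text does not support that: it is randomised, contemporaneous, and made by experienced observers in both arms. No before-after estimate is planned to compete with it, so calling the first NOST round a baseline is mainly a matter of naming.
- **Other outcomes differ.** The Intervention section's sentence also covers outcomes with control data over time: patient registry data on both arms from before NOST started, and routinely collected surveillance and outbreak data. The single-measurement objection does not apply to them.
- **Season is partly matched.** The first and one-year rounds fall at about the same time of year, so season mainly disturbs the rounds between. Secular trend and observer experience are not removed.

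The schedule in Figure 1 is not shown in the text reviewed, but the wording consistently gives one control measurement. None of this makes the compliance series informative about a change in effect.

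**Conclusion.** The point holds for hand hygiene compliance only. As written, the protocol draws from one arm a conclusion that its own definition of effect requires two arms to support. The within-arm series shows a change in compliance level and cannot show a change in effect.

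That conclusion follows from the measurement schedule and needs no assumption about drift. The size does: 15% to 50% of the hypothesised effect rests on an assumed drift of 0.03 to 0.10 over the year, and the true drift could be smaller, larger or in either direction. The point should not be read as a flaw in the one-year randomised estimate or in the follow-up of registry outcomes. It is a limited correction, worth making because the claim is stated twice and has no method behind it.

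**What to change.** **Protocol, Data collection and outcomes.** Replace the sentence on repeated measurements with text such as: *Repeated measurements in the intervention wards will describe measured compliance over time in NOST wards. The only effect estimate for compliance is the randomised contrast at one year. No growth, persistence or waning of the effect on compliance will be concluded from the within-arm series.*

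**Protocol, Intervention.** Split the follow-up sentence. Compliance is described over time in NOST wards. For registry outcomes, any statement about a change in effect over time compares intervention with control wards over the same periods. Their follow-up stays, as does their measurement over the one-year period in SAP section 5.2.

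**Cost.** Wording only. The trial gives up a durability claim for compliance that its data cannot support.

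Keeping that claim would need control measurements at the same rounds. This removes the bias but raises the standard error by √2. Under the step 5 assumptions, the change in effect detectable with 80% power would be about 0.12 at 26 wards per arm and 0.05 at 150 (0.16 and 0.065 with 50% carry-over). It would also expose control wards to observation, which the protocol counts as part of the intervention. The wording change is the proportionate choice.

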In addition, we will apply for data from the Norwegian Patient Registry (NPR) for patients admitted to intervention or control wards during the study period. We will use the number and proportion of patients diagnosed with infection defined as HAI (according to European definitions used in NOIS), and the number of days hospitalized per stay.

A summary of the type of data and outcome measures is shown in Table 1.

Table 1. Data and outcome measures used to evaluate the impact of NOST on compliance with hand hygiene recommendations and the occurrence of HAI and outbreaks in hospitals

Numerator Denominator Outcome measure per arm		Numerator	Denominator	Outcome measure per arm
-----------------------------------------------	--	-----------	-------------	-------------------------

Hand hygiene observations	Number of hand hygiene performed on indicated events	Number of indicated events observed	Proportion of correct compliance, in total and by occupation
Outbreaks of infectious diseases (VESUV)	 Number of outbreaks Number of infected patients and staff 	 Number of wards Number of inpatients Number of full-time positions 	 Proportion of outbreaks per ward Secondary attack rate (SAR) by inpatients and staff
Surveillance of HAI (NOIS)	 Number of infected patients Number of patients treated with antibiotics 	Number of inpatients	Proportion of infected inpatients by type of infections
Surveillance of postoperative site infections (NOIS-POSI)	Number of patients with postoperative site infections	Number of surgical patients	Proportion of infected patients by type of surgery and type of infections
HAI-diagnoses (NPR)	Number of patients with infections defined as HAI	Number of bed-days	Number of infected patients per 1000 patient days, by type of HAI
Length of stay (NPR)	Number of bed- days per patient per stay	Number of hospital stays	Mean and median bed-days per stay

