The number of outbreaks per arm will be collected from VESUV. At the start of the evaluation period, we will ask participating hospitals to submit the number of full-time positions per included ward. The number of inpatients per ward per day will be obtained from NPR. The number of positions and inpatients will be used as denominators when estimating the secondary attack rate in outbreaks. The number of patients registered in NOIS will be compared to the number of daily inpatients registered in NPR. If the number of inpatients per day changes over time, we will make a new collection of the number of full-time positions to capture significant changes in the organization and size of included wards.

NOIS and NOIS-POSI are surveillance systems where numerators and denominators are registered. From these systems, it is sufficient to receive the results for each ward in the form of the proportion of patients with different types of infections.

From NPR, we will apply for data for all hospitalized patients at both intervention and control wards from and including 1. January 2020 up to the time of application in 2024, giving numerators and denominators for the periods before, during and after the intervention.

When comparing intervention and control groups, we will estimate relative risk (RR) and absolute risk difference (ARF) with 95% confidence intervals (table 2). We will report two-sided p-values where applicable and use the significance criterion p<0.05.

We will use modified Poisson regression to compare hand hygiene compliance one year after NOST was introduced in the intervention wards³. We will adjust for the factor used in stratification (hospitals) as a fixed effect.

Compliance will be analyzed and reported for each occupational group and total for all healthcare personnel. Outbreaks will be analyzed and reported as the number of outbreaks and secondary attack rate per arm, in total and distributed by patients and staff. The incidence of infection in patients will be analyzed and reported in total and by types of infection.

A more detailed description of the analyzes of the main and secondary outcomes will be published in a separate analysis plan.

[figure not shown]

Figure 1. Overview and schedule for the intervention and measurements in the evaluation

Table 2. Dummy table with results for compliance with hand hygiene recommendations

	Intervention arm	Control arm	ICC	Adjusted RR (95% CI)	ARF (95% KI)	p-value
Primary outcome						

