In this project, we will not register or collect direct identifiable personal data. In the hand hygiene observations, only the events and occupation are recorded, but not personal data on the people observed. Furthermore, we will only ask for statistics from VESUV and NOIS/NOIS-POSI. This data will include the number of people infected in outbreaks per ward distributed by employees and inpatients, as well as the number of inpatients with relevant types of infection in the surveillance of HAI. These data are regularly published at the hospital level. We will apply for data from NPR that includes information on each patient admitted to the relevant wards in the period from 1 January 2022 to mid-2024. However, we will ask for data without directly personally identifiable information (data without name and social security number).

Together with the data protection officer at NIPH, we will perform a data protection impact assessment (DPIA) related to the collection and handling of data in the project.

References

- 3. Zou G. A modified poisson regression approach to prospective studies with binary data. *Am J Epidemiol* 2004; **159**(7): 702-6.

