The primary outcome is compliance with hand hygiene recommendations by hospital employees who do patient-related work. Compliance will be assessed one year after randomization by trained and experienced observers. The observers will record the number of observations made and the number of these observations that meet the criteria for compliance. The number of observations and compliances will be measured at the level of hospital ward. Compliance will therefore be aggregated at the level of hospital ward and the primary outcome is a count variable.

161 **5.2 Secondary outcomes**

As for the primary outcome, all secondary outcomes will be aggregated at the level of hospital ward.
Unlike the primary outcome, all secondary outcomes are measured over the one-year trial period
rather than at the end of the trial.

165

Sec	ondary Outcome	Туре	Denominator	Data source			
Infe	Infectious disease outbreaks						
1.	Outbreak	Count	Wards	VESUV			
2.	Inpatient infection	Count	Inpatients in wards with outbreaks				
3.	Employee infection	Count	Employees in wards with outbreaks				
Sur	veillance of HAI						
4.	Inpatient infection	Count	Inpatients included in	NOIS			
			the surveillance				
5.	Inpatient antibiotic treatment	Count	Inpatients included in				
			the surveillance				
Sur	veillance of postoperative site infectior	15					
6.	Inpatient treatment for postoperative	Count	Surgical inpatients	NOIS-POSI			
	site infection		included in the				
			surveillance				
HAI	diagnoses						
7.	Inpatient HAI diagnosis	Count	Inpatients in the study period	NPR			
Len	gth of hospital stay						
8.	Bed-days per inpatient per stay	Continuous		NPR			

166 167

168 6 Sample Size

169 Assuming $\alpha = 0.05$, $\beta = 0.8$, a control risk of 0.4, an intervention risk of 0.6 (i.e., the treatment effect 170 is a risk difference of at least 0.2), an ICC of 0.1, an average cluster size of 30 observations among 171 hospital employees who do patient-related work, a loss of 2 d.f. for adjustment of cluster-level 172 covariates, and stratification by hospital, it was estimated that at least 52 hospital wards should be 173 recruited (26 in each arm).

7 General Analysis Considerations

175 **7.1 Timing of Analyses**

176 Analyses will be performed after the database is locked. No interim or follow-up analyses are planned.

177 7.2 Analysis Sets

Although this SAP defines three populations, there is only a single analysis set that will contain all

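### Employee infection in outbreaks (SAP 10.2.3): cases are persons and the SAP denominator is employees, but the only staff denominator collected is full-time positions

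*Protocol*

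**What the plan says.** **Numerator.** The protocol's Ethics section describes the VESUV data as the "number of people infected in outbreaks per ward distributed by employees and inpatients". These are persons.

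**Denominator collected.** Under Data collection and outcomes, at the start of the evaluation period, "we will ask participating hospitals to submit the number of full-time positions per included ward". Table 1 lists "Number of full-time positions" as the staff denominator for outbreaks, and the text confirms its use: "The number of positions and inpatients will be used as denominators when estimating the secondary attack rate in outbreaks". If the daily number of inpatients changes, "we will make a new collection of the number of full-time positions to capture significant changes"; that repeat request is again for positions.

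**Denominator in the SAP.** The outcome table in SAP 5.2 gives "Employees in wards with outbreaks", with VESUV as the data source. SAP 10.2.3 defines the estimand as a risk of employee infection over one year, restricts the analysis to wards with a reported outbreak, and reports a risk ratio (RR) and an indicative risk difference (RD). SAP 9.1 fits n_i as binomial with N_i trials and a log link.

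Neither document says where a count of employees would come from, defines full-time positions, or gives a headcount or part-time share.

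**The concern.** A binomial risk needs the same unit above and below the line. Here the cases are people, the estimand is per person, and the only staff denominator planned for collection is a measure of staffing volume. Part-time staff can each become a case but may add only a fraction of a position to the denominator; temporary or rotating staff may add nothing.

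The SAP announces its other departures from the protocol: the added ward population (4.2) and the dropped hospital fixed effect (7.3). It does not mention this change of denominator. The analyst is left either to use positions as N_i, as the protocol says, or to find an employee count that nobody has planned to collect. At stake are the absolute staff risk and the RD, possibly the RR, and in extreme cases the validity of the binomial likelihood.

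**Working it through.** The documents state no staff risk, headcount, number of positions or part-time share, so there is no plan figure to reproduce. Every ratio and attack rate below is an assumption, used to show a range.

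**Notation.** k = headcount / positions in a ward or arm. With positions as N_i:

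- apparent risk = k × true risk
- apparent RR = true RR × (k_NOST / k_control)
- indicative RD (SAP 9.1) = apparent control risk × (apparent RR − 1), so with equal k in both arms it is k × true RD

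**Absolute risk, true value 0.30.**

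- k = 1.1: 1.1 × 0.30 = 0.33
- k = 1.25: 1.25 × 0.30 = 0.375
- k = 1.5: 1.5 × 0.30 = 0.45

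**RR and RD, true risks 0.20 (control) and 0.15 (NOST), so RR 0.75 and RD −0.05.**

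| k control | k NOST | apparent risks | RR | RD |
|---|---|---|---|---|
| 1.25 | 1.25 | 0.25 and 0.1875 | 0.75 | −0.0625 |
| 1.5 | 1.5 | 0.30 and 0.225 | 0.75 | −0.075 |
| 1.2 | 1.4 | 0.24 and 0.21 | 0.875 | −0.03 |
| 1.4 | 1.2 | 0.28 and 0.18 | 0.643 | −0.10 |

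An equal ratio leaves the RR alone and inflates the RD. Unequal ratios move both, in either direction.

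**Can cases exceed N_i?** Take a ward with 30 staff, let X be binomial with 30 trials at the stated attack rate, and compute the probability that X exceeds the number of positions.

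| positions (k) | attack rate 0.30 | 0.50 | 0.70 |
|---|---|---|---|
| 24 (1.25) | practically 0 | 0.00016 | 0.077 |
| 20 (1.5) | 0.00001 | 0.021 | 0.59 |
| 15 (2.0) | 0.006 | 0.43 | 0.98 |

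At an attack rate of 0.10 the probability is practically zero for every ratio tried. These figures treat infections as independent. Within-ward transmission would fatten the tail for a given average attack rate. In a test log-binomial fit with one ward at n = 22 and N = 20, the log-likelihood was minus infinity although the routine reported convergence. Stata and R, which the SAP names, were not tested.

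**Fractional positions.** Position totals need not be whole numbers. SAP 7.5 treats non-integer entries for counts as miscoded, so a correctly reported fractional total would be queried as an error.

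**The case against.** The strongest reply is that the SAP governs the analysis. The protocol defers the detail of the secondary outcomes to it, and it says employees, not positions. Read that way, the defect is a denominator without a source, not a biased one. This stands in part: a reader might infer that staff risks are overstated as a matter of fact, and the documents do not support that. Overstatement requires that positions are used as N_i and that headcount exceeds positions; vacant posts would push the other way. But the SAP withdraws nothing in the protocol's explicit rule, and positions are the only staff figure that will be on file.

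Second, RR is the modelled measure, RD is only indicative, and wards are randomized 1:1 within hospital, so k should balance in expectation. This also stands in part. A reader might infer that the RR is biased, or that wards are too few to balance; the protocol expects several hundred, and nothing in the documents shows unequal k. However, the analysis set is wards with a reported outbreak, a subset formed after randomization and of unknown size, where balance is not guaranteed. The absolute risk and the RD gain no protection from balance.

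Third, model failure is an edge case. That is correct: it needs a high attack rate together with a high ratio, and it should not be presented as likely.

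Finally, a reader might add that index cases are wrongly included, because the protocol's Study populations section speaks of the "number of secondary cases in outbreaks" while Table 1 counts all infected patients and staff. The SAP has largely overtaken this: its outcome is infection as part of an outbreak, and its outcome table and estimands do not use the term secondary attack rate. Where the index case is a patient, the staff count contains no index case anyway. What remains is a label to align.

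**Conclusion.** The mismatch is real and visible in the text: the protocol's stated denominator is in the wrong unit for the SAP's estimand and model, and no headcount is planned. If positions are used, the staff risk is wrong by the factor k wherever k differs from 1, and with equal k in both arms so is the indicative RD: by 10% to 50% over the assumed range 1.1 to 1.5. The RR is affected only through a difference in k between arms. Cases exceeding N_i is possible but unlikely outside large outbreaks in wards where headcount is well above positions.

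The scope is one of eight secondary outcomes, analysed only in outbreak wards. The primary outcome and the sample size do not depend on it. It is still worth correcting, because without an employee count the estimand in SAP 10.2.3 cannot be computed from the data planned.

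**What to change.** 1. In the request that already asks hospitals to "submit the number of full-time positions per included ward", also ask for the number of persons doing patient-related work in each ward. Keep positions as a supplement and define the term.
2. In SAP 5.2 and 10.2.3, name that headcount as the source of N_i, and change the protocol's sentence on denominators to agree.
3. If only positions can be obtained, report infections per position from a count model (for example Poisson with log positions as offset and hospital-clustered robust standard errors), and do not call the result a risk.
4. Align the outbreak label in the protocol's Table 1 with the SAP's outcome name.

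The cost is one extra number per ward and a line in each document. Limits remain. A headcount at one date misses turnover and temporary staff, and the planned re-collection, being triggered by inpatient numbers, does not fully address this. Headcount guarantees n_i ≤ N_i only if each case belongs to the counted staff and nobody infected in two outbreaks during the year is counted twice.
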